1.2 Secondary Objectives

- a. To compare overall survival (OS) in patients randomized to extended PLND versus those randomized to standard pelvic lymphadenectomy.
- b. To evaluate operative time, whether or not nerve sparing was performed, intra-operative, peri-operative and 90 day morbidity and mortality, length of hospital stay, histology (pure urothelial versus mixed), lymph node counts and lymph node density, adjuvant chemotherapy received, and local and retroperitoneal soft tissue recurrence in patients randomized to extended PLND versus those randomized to standard pelvic lymphadenectomy. Proximal extent of node dissection in those patients randomized to extended PLND will be evaluated as well.

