7.7 Follow-Up Period

All patients will be followed for recurrence and survival for a maximum of 6 years after Step 2, Randomization or until death (whichever occurs first).

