10.4 Overall Survival

Measured from date of randomization to date of death from any cause. Patients known to be alive are censored at date of last contact.

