11.0 STATISTICAL CONSIDERATIONS

11.1 Accrual Goal

We anticipate that 113 eligible patients will be randomized per year to this study on a group-wide basis. We will also assume that 10 percent of enrolled patients will be found to be clinically or pathologically ineligible and hence, not randomized so our Step 1 sample size will be inflated to account for this. Based on an extensive review of the contemporary literature (see [Section 2.0, Table 1](#)), we estimate that 3-year disease free survival (DFS) for patients at increased risk for pelvic and iliac node metastasis undergoing a standard pelvic lymphadenectomy is 55%. A poll of centers of excellence suggest that a 10-12% improvement in 3-year DFS (65-67%) for patients in extended lymphadenectomy would be meaningful and establish extended node dissection as the standard of care in this patient population. Assuming exponential survival, 5 years of patient accrual, 3 additional years of follow-up and a sample size of 564 eligible patients (282 per arm), the study has 85% power to detect a 28% reduction in the hazard rate of progression or death with extended lymph node dissection compared to limited

dissection (hazard ratio 0.72). This corresponds to an improvement in 3-year DFS from 55% to 65% or alternatively median DFS would be extended from 3.5 to 4.8 years if the DFS distributions are exponential. We will use a one sided stratified log rank test with $\alpha = 0.025$, and the analysis will be intent-to-treat.

Assuming an ineligibility rate of 10%, total accrual (eligible + ineligible patients) to the initial step is expected to be 620 patients.

As a secondary endpoint, overall survival is also of great interest. If extended lymph node dissection is found to be statistically significantly better than standard lymph node dissection with respect to DFS, then an analysis of the survival endpoint will follow. We will allow for three more years of follow-up after the primary analysis has been conducted to assess potential survival differences. If we assume that the standard arm has 5-year survival of 55% then we will have 83% statistical power to detect a hazard ratio of 0.72 (55% vs. 65% survival at 5 years) using a one-sided stratified logrank test with alpha=0.025.

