If this trial continues past the two feasibility assessments, three formal interim analyses are planned to evaluate the efficacy of extended lymph node dissection. The first will be conducted after 25% of the expected events (relapse or death without relapse) have been reported on the control arm. The second after 50% of the events have occurred on the control arm, and the third when 75% of the expected events have occurred on the control arm. See the [table](#) for number of events and expected time when events will occur. The interim analyses will be conducted based on the number of events in the standard LND arm and not the estimated calendar time. Estimated number of events in the experimental arm are provided for descriptive purposes only. At each interim analysis, evidence suggesting early termination of the trial and a conclusion that the extended lymph node dissection is no better than standard dissection would be if the alternative hypothesis of a 28% improvement in DFS with the experimental arm is

rejected at the 0.005 level, using an extension of the logrank test that allows for testing a relative risk not equal to 1. In addition, the null hypothesis of no difference in DFS will be tested at the one-sided level of 0.005. If the decision is to continue the study for the full specified period, we estimate the final analysis will occur approximately three years after completion of accrual. The final DFS analysis will be conducted when 184 events have been observed on the standard LND arm, using a one-sided stratified logrank test with a significance level of 0.022 to account for multiple interim testing.

If the DFS analysis is statistically significant, the survival analysis will follow approximately two years later when 166 deaths have occurred on the control arm. The stratified logrank test will be performed at the one-sided 0.025 level.

Interim Analysis	Anticipated Analysis Time Relative to Study Activation	Percent of Expected Information On Control Arm	# of Events in the Control Arm (Standard LND)	Anticipated # of Events on Experimental Arm (Extended LND) (assuming the alternative hypothesis)
1	38 months	25%	46	34
2	56 months	50%	92	70
3	73 months	75%	139	108

With 282 eligible patients randomized to each arm, estimates of morbidity and toxicity frequencies can be estimated to within \pm 6% (95% confidence interval).

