In addition to formally testing DFS at the interim analyses, the DSMC will also consider the secondary endpoints of morbidity (intra-operative and up to 90 days post-operatively) and survival.

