14.4 Data Submission Overview and Timepoints

- a. WITHIN 7 DAYS OF STEP 1, REGISTRATION:

Submit the following:

S1011 Prestudy Form

Operative Report from TURBT

Pathology Report from TURBT

Radiology reports from cross-sectional imaging performed to determine the pre-REG clinical T stage, e.g. CT, MRI, or PET/CT.

- b. WITHIN 14 DAYS OF SURGERY, FOR ALL PATIENTS RECEIVING ON-STUDY SURGERY:

Submit copies of the following:

S1011 Intra-Op Surgical Assessment Form Standard Versus Extended LND

Intra-Op Photos

(Note: The Photo Upload Form is located in the data submission section of the SWOG CRA Workbench in the **S1011** Reg 2 folder under the 'Follow Up' tab. Photos should be obtained after the randomization and surgical assessment).

Operative Report from cystectomy

Pathology Report from cystectomy

- c. IF PATIENT CONSENTED, WITHIN 28 DAYS OF RANDOMIZATION:

Submit specimens as outlined in [Section 15.0](#).

- d. IF PATIENT NOT ELIGIBLE OR NOT CONTINUING TO STEP 2 RANDOMIZATION, WITHIN 14 DAYS AFTER GOING OFF STUDY:

S1011 Pre-Randomization Off Study Form

S1011 Intra-Op Surgical Assessment Form Standard Versus Extended LND
(Note: No Intra-Op photos are required for patients not going on to Step 2, Randomization)

e. WITHIN 7 DAYS FROM HOSPITAL DISCHARGE:

S1011 Surgeon's Post-Op Data Form Standard Versus Extended LND

S1011 Adverse Event Form

f. WITHIN 90 DAYS POST-SURGERY

S1011 Surgeon's 90-Day Assessment Form Standard Versus Extended LND

S1011 Adverse Event Form

g. AFTER SURGERY, EVERY THREE MONTHS FOR YEAR ONE; EVERY SIX MONTHS FOR YEARS TWO AND THREE; AND ANNUALLY UNTIL SIX YEARS AFTER RANDOMIZATION OR UNTIL DEATH:

Submit copies of the **S1011** Follow Up Form
(via the Medidata Rave® clinical data management system)

h. WITHIN 4 WEEKS OF KNOWLEDGE OF DEATH:

Submit the Notice of Death **and a final S1011** Follow Up Form.
(via the Medidata Rave® clinical data management system)

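### The overall survival test waits for 166 control deaths, but six-year follow-up is expected to give about 144; and no final OS estimate is written if DFS shows no significant benefit

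*Combined protocol and SAP*

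**What the plan says.** Secondary objective 1.2a is unconditional: "To compare overall survival (OS) in patients randomized to extended PLND versus those randomized to standard pelvic lymphadenectomy".

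The only final OS analysis by arm is conditional, and it is written twice.
- Section 11.1: "If extended lymph node dissection is found to be statistically significantly better than standard lymph node dissection with respect to DFS, then an analysis" of survival follows. Its timing there is: "We will allow for three more years of follow-up after the primary analysis has been conducted to assess potential survival differences". The stated power is 83% at a hazard ratio of 0.72, with 55% five-year control OS and one-sided alpha 0.025.
- Section 11.2: "If the DFS analysis is statistically significant, the survival analysis will follow approximately two years later when 166 deaths have occurred" on the control arm.

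Follow-up is limited elsewhere.
- Section 7.7: "All patients will be followed for recurrence and survival for a maximum of 6 years after Step 2, Randomization or until death".
- Section 14.4g schedules follow-up forms "ANNUALLY UNTIL SIX YEARS AFTER RANDOMIZATION OR UNTIL DEATH".
- The last column of the study calendar (9.0) is month 72.
- Section 10.4: "Patients known to be alive are censored at date of last contact".

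During the trial, 11.2 adds: "In addition to formally testing DFS at the interim analyses, the DSMC will also consider the secondary endpoints of morbidity" and survival. Section 11.3 compares mortality only around surgery and at 90 days. Section 11.4 analyses survival by tissue marker, not by arm.

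**The concern.** There are two separate points.

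1. **Trigger and power.** The OS test is tied to a death count that looks as if it was derived with open-ended follow-up, while the protocol stops following each patient at six years. If so, a positive DFS result would be followed by an OS test that waits for events the trial is not set up to observe, with less power than stated.
2. **No final OS estimate unless DFS shows benefit.** The background (2.0) says that morbidity from extended dissection could outweigh its benefit. It also cites a pancreatic cancer trial that closed with poorer survival in the extended arm. After a neutral or adverse DFS result, readers would want to know which OS differences the data exclude. Without a written rule, whether and when OS is reported would be settled after the DFS result is known.

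**Working it through.** **Inputs.** From 11.1: 282 patients per arm, 5 years of accrual, DFS analysis 3 years later, 55% three-year control DFS, 55% five-year control OS, hazard ratio 0.72, one-sided 0.025. From 7.7 and 14.4g: a six-year limit per patient. Assumed: uniform accrual, exponential survival and no loss to follow-up (none is stated; any loss lowers the death counts).

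**Formulas.** Expected events = 282 × the average over entry times of 1 − exp(−λf), where f is a patient's follow-up. Power = Φ(−ln 0.72 × √(D/4) − 1.96), where D is deaths in both arms.

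**Reproducing the plan without the limit**
- DFS: λ = −ln(0.55)/3. At year 8 this gives 183.8 control events (plan: 184) and 335 in total, with 85.2% power (plan: 85%). The interim times come out at 37.9, 56.1 and 73.4 months (plan: 38, 56, 73).
- OS: λ = −ln(0.55)/5 = 0.1196 per year. At year 10 (two years after the DFS analysis) this gives 165.3 control deaths (plan: 166). D = 165.3 + 133.0 = 298.3, and power is 81.0%.
- At year 11 (three years after), D = 178.4 + 145.3 = 323.7 and power is 84.0%. The stated 83% needs about 315 deaths.

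So 166 and 83% fit the plan's assumptions when follow-up has no six-year limit.

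**With the six-year limit**
- Control deaths at completed follow-up (year 11): 282 × (1 − 0.55^(6/5)) = 282 × 0.512 = 144.4, which is 22 short of 166.
- Experimental deaths at hazard ratio 0.72: 113.8. D = 258.1 and power is 75.1%.
- 166 deaths is 166/282 = 58.9% six-year mortality, which means a five-year control OS of (1 − 0.589)^(5/6) ≈ 47.7%.

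**Sensitivity to control OS** (limit applied; chance from the binomial tail with n = 282)

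| Five-year control OS | Expected control deaths | Chance of 166 or more | Power at HR 0.72 |
|---|---|---|---|
| 60% | 129 | under 0.1% | 70% |
| 55% (plan) | 144 | 0.6% | 75% |
| 50% | 159 | 23% | 79% |
| 45% | 174 | 85% | 83% |

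Table 2 of the background lists all-patient five-year OS from 45% to 66%.

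**Timing.** Completed follow-up falls at year 11. If the limit is ignored for DFS, the final DFS analysis is at year 8, three years earlier. If it is applied to DFS as well, year 8 gives about 178 control DFS events and 184 are reached at about 8.5 years, so the gap is about 2.5 years.

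**How often no final OS analysis is written.** This was simulated from the looks at 46, 92, 139 and 184 control events, with one-sided 0.005 boundaries for benefit and for lack of benefit at the interims and 0.022 at the end, both followed. The condition for OS is not met in about 16% of trials at DFS hazard ratio 0.72, 47% at 0.80, 83% at 0.90 and 97% at 1.0. At 1.0 about 60% stop early for lack of benefit.

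**What an estimate would show.** If OS is equal in the arms, with d deaths per arm, the 95% interval is exp(±1.96 × √(2/d)).
- Stopped at look 1 (about 30 per arm): 0.60–1.66. If accrual ends there and those patients complete six years (178.6 × 0.512 = 91.4 per arm): 0.75–1.34.
- Final DFS look: 0.78–1.28 at year 8 (128 per arm), or 0.79–1.27 at year 8.5 (133 per arm).
- Full accrual, completed follow-up (144 per arm): 0.79–1.26.

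**The case against.** **On the trigger.** Section 11.1 makes a specific provision for more follow-up after the primary analysis, and 14.4h asks for a death notice whenever a death becomes known, with no six-year limit. If 11.1 governs, the trigger and power are coherent, as the reproduction shows. An allowance of three years and an event trigger expected at about two need not conflict. This stands to the extent that the defect is a contradiction between sections, not faulty arithmetic in 11.1. It does not remove the contradiction: 7.7 covers survival explicitly, the calendar and 14.4g agree with it, and death notices without scheduled contact after year 6 would not give complete follow-up.

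A reader might infer that 166 deaths cannot be reached. The documents do not support that: at 45% five-year OS, the lowest series in Table 2, it would probably be reached. Nor does the limit block the DFS trigger, since completed follow-up gives 282 × (1 − 0.55²) ≈ 197 control DFS events against 184.

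**On the missing estimate.** Testing OS only after a significant DFS result is a valid way to control type I error. Nothing forbids reporting OS otherwise, deaths count in DFS, and the monitoring committee sees survival at the interims. All of this stands, and it makes this the weaker point. Three stronger readings fail.
- That every early stop leaves OS unanalysed: a stop for efficacy meets the condition as 11.1 words it, although its OS timing then rests on the same 166 deaths.
- That the 97% at hazard ratio 1.0 measures harm: it is type I error control at work.
- That the stopping percentages are fixed: 11.2 words the lack-of-benefit rule as evidence suggesting termination, and 11.5 leaves the decision to the committee.

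**Conclusion.** The trigger and power are wrong as written: they conflict with the plan's own follow-up rule. Under the six-year limit and 55% five-year control OS, about 144 control deaths are expected against 166, and power is about 75% against 83%. This rests on exponential survival, uniform accrual and no dropout. The 0.6% chance of reaching 166 holds only at 55%, and the sensitivity table should be read with it.

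The second point also holds, with less weight. The only final OS analysis by arm depends on a significant DFS benefit, although objective 1.2a has no condition. It covers a neutral DFS result, an adverse one, and a stop for lack of benefit. It is a gap in what is written, not an error in the testing order. Both points should be corrected.

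**What to change.** **1. Reconcile 7.7, 14.4g, 11.1 and 11.2, choosing one of:**
- Keep the six-year limit. Drop the 166-death trigger, time the OS test to completed follow-up of all randomized patients (about year 11, some 2.5 to 3 years after the DFS analysis, depending on whether the limit is also applied to DFS), and restate power as about 75%. The cost is wording and a lower stated power.
- Keep 166 deaths and 83% power. Extend survival follow-up in 7.7 and 14.4g to match. The cost is longer follow-up for survival.

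Either way, give one timing in place of the two in 11.1 and 11.2.

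**2. Add to 11.1 and 11.2:** whatever the DFS result, OS will be estimated by arm (Kaplan-Meier curves, stratified hazard ratio, two-sided 95% confidence interval) at the DFS analysis that ends the trial, and again when all randomized patients have completed six-year follow-up. These are estimates; only the formal one-sided 0.025 test is conditional on a significant DFS result. The second estimate matters most after an early stop for lack of benefit, and it requires follow-up to continue to six years, as 7.7 already provides. The cost is wording only: no alpha is spent and no new data are needed. The downside is that an unconditional estimate could be over-read, so it must be labelled as estimation.

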11.2 Analysis of Primary Endpoint

The trial will first open to selected sites with high volume cystectomy practices (more than 30 per year). Each surgeon will be credentialed for enrolling in this vanguard lead-in based on review of case logs, operative and pathology reports as well as photographic documentation of competence in performing a pelvic and iliac lymphadenectomy including standard pelvic plus bilateral common iliac and pre-sacral nodes. Rationale: to monitor quality control – a) ability to consistently perform extended node dissection and completeness of the standard dissection; b) make necessary modifications to protocol if needed; c) to monitor effects of neoadjuvant chemotherapy and consistency of adjuvant chemotherapy; d) to monitor any morbidity attributable to extended node dissection.

A first feasibility analysis would be conducted after the first 15 patients have been randomized. This analysis will address the feasibility and measurement quality of the video and/or photographic documentation of the nodal dissections at each institution by surgeon. The Study Chairs anticipate that the intra-operative photography will be of sufficient quality to credibly demonstrate the expected completeness of the node dissection. The video and/or photographs will be analyzed for compliance with the stated boundaries of the nodal dissection and feed-back will be given to each center based on this feasibility analysis. Operative and pathology reports will be analyzed for consistency with the photographic documentation.

The second feasibility analysis would be conducted 1 year after all vanguard sites have IRB approval of this study at which time it is expected that approximately 100 patients will have been enrolled. If the planned accrual rate of 100 patients is not met, consideration will be given to closing the study due to lack of feasibility. However, this is just a guideline and there may be extenuating circumstances related to, for example, delays in IRB approval that might also be considered. If the study does reach this initial accrual goal, it would be opened up more broadly to other qualifying centers.

If this trial continues past the two feasibility assessments, three formal interim analyses are planned to evaluate the efficacy of extended lymph node dissection. The first will be conducted after 25% of the expected events (relapse or death without relapse) have been reported on the control arm. The second after 50% of the events have occurred on the control arm, and the third when 75% of the expected events have occurred on the control arm. See the [table](#) for number of events and expected time when events will occur. The interim analyses will be conducted based on the number of events in the standard LND arm and not the estimated calendar time. Estimated number of events in the experimental arm are provided for descriptive purposes only. At each interim analysis, evidence suggesting early termination of the trial and a conclusion that the extended lymph node dissection is no better than standard dissection would be if the alternative hypothesis of a 28% improvement in DFS with the experimental arm is

rejected at the 0.005 level, using an extension of the logrank test that allows for testing a relative risk not equal to 1. In addition, the null hypothesis of no difference in DFS will be tested at the one-sided level of 0.005. If the decision is to continue the study for the full specified period, we estimate the final analysis will occur approximately three years after completion of accrual. The final DFS analysis will be conducted when 184 events have been observed on the standard LND arm, using a one-sided stratified logrank test with a significance level of 0.022 to account for multiple interim testing.

If the DFS analysis is statistically significant, the survival analysis will follow approximately two years later when 166 deaths have occurred on the control arm. The stratified logrank test will be performed at the one-sided 0.025 level.

Interim Analysis	Anticipated Analysis Time Relative to Study Activation	Percent of Expected Information On Control Arm	# of Events in the Control Arm (Standard LND)	Anticipated # of Events on Experimental Arm (Extended LND) (assuming the alternative hypothesis)
1	38 months	25%	46	34
2	56 months	50%	92	70
3	73 months	75%	139	108

With 282 eligible patients randomized to each arm, estimates of morbidity and toxicity frequencies can be estimated to within \pm 6% (95% confidence interval).

In addition to formally testing DFS at the interim analyses, the DSMC will also consider the secondary endpoints of morbidity (intra-operative and up to 90 days post-operatively) and survival.

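### Section 11.2 lets an interim rejection of HR 0.72 support the conclusion that extended dissection is no better than standard, which that test does not show

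*Combined protocol and SAP*

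**What the plan says.** Section 11.2 plans three interim analyses, triggered by control-arm events: "The interim analyses will be conducted based on the number of events in the standard LND arm and not the estimated calendar time". Its table gives 46, 92 and 139 control events, with 34, 70 and 108 expected on the extended arm under the alternative.

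Two tests are run at each look.

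- **Futility.** The trial may stop if "the alternative hypothesis of a 28% improvement in DFS with the experimental arm is" then "rejected at the 0.005 level, using an extension of the logrank test that allows for testing a relative risk not equal to 1". The plan describes this outcome as "evidence suggesting early termination of the trial and a conclusion that the extended lymph node dissection is no better than standard dissection".
- **Efficacy.** Separately, "the null hypothesis of no difference in DFS will be tested at the one-sided level of 0.005".

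The efficacy test is called one-sided. The futility sentence gives no sidedness. The end of Section 11.2 has the monitoring committee also consider morbidity and survival, and Section 11.5 makes the committee responsible for decisions on termination and early reporting.

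**The concern.** The futility test and its conclusion concern different hypotheses. Rejecting a hazard ratio of 0.72 says that the benefit is smaller than the design target. Saying that extended dissection is no better than standard is a statement about a hazard ratio of 1 or more, and nothing in the futility rule tests that. The plan tests the null of no difference separately, so it recognises these as two hypotheses, yet it words the futility conclusion as if rejecting one settled the other.

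The distinction matters here. Section 2.0 presents the trial as randomised evidence on how extensive the dissection should be, and notes that added morbidity could outweigh a benefit. For that trade-off, a benefit below 28% and no benefit at all are different inputs. A real but smaller effect could be labelled as no benefit.

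**Working it through.** **Design check.** Section 11.1 gives 282 patients per arm, 5 years of accrual, 3 further years of follow-up, exponential DFS and 55% control DFS at 3 years. The control hazard is −ln(0.55)/3 per year. With uniform accrual, expected events are 183.8 (control) and 151.1 (extended, HR 0.72), 335 in total. Schoenfeld power at one-sided 0.025 is 85.2%. The plan's 85% power and 184 control events are reproduced.

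**Boundary.** With d total events, the standard error of the log hazard ratio is about 2/√d. The rule fires when the observed hazard ratio is at least

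HR_b = 0.72 × exp(z × 2/√d),

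and the 95% limits at that point are HR_b × exp(±1.96 × 2/√d). I take z = 2.576 if the 0.005 is one-sided and 2.807 if it is two-sided.

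**Event counts.** The table's extended-arm counts assume HR 0.72, which is too few for a trial sitting on the futility boundary. I therefore show a range from the table totals (46 + 34 = 80; 92 + 70 = 162; 139 + 108 = 247) to equal events per arm (92, 184, 278).

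Example, third look with 278 events, one-sided: 2/√278 = 0.120; HR_b = 0.72 × exp(2.576 × 0.120) = 0.98; lower limit 0.98 × exp(−1.96 × 0.120) = 0.78 (0.775 before rounding).

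| Look | Total events | One-sided: HR_b | Lower 95% limit | Two-sided: HR_b | Lower 95% limit |
|---|---|---|---|---|---|
| 1 | 80-92 | 1.28-1.23 | 0.83-0.82 | 1.35-1.29 | 0.87-0.86 |
| 2 | 162-184 | 1.08-1.05 | 0.79 | 1.12-1.09 | 0.82 |
| 3 | 247-278 | 1.00-0.98 | 0.78 | 1.03-1.01 | 0.80 |

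At every look and under either reading, the interval at the boundary includes hazard ratios below 1. A lower limit of 0.78 corresponds to 3-year DFS of 0.55^0.78 = 62.7%, against 55% on control.

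**Chance of a futility stop.** Simulated with looks at 46, 92 and 139 control events and the 0.005 efficacy rule in force:

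| True HR | 3-year DFS, extended arm (0.55^HR) | One-sided 0.005 | Two-sided 0.005 |
|---|---|---|---|
| 0.80 | 62% | 6% | 4% |
| 0.85 | 60% | 14% | 10% |
| 0.90 | 58% | 27% | 20% |

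**Observed hazard ratio below 1.** In patient-level simulation with a one-sided test, the lowest hazard ratios that fired the rule were about 1.19, 1.04 and 0.98 at looks 1 to 3. A first stop with an estimate below 1 occurred only at the third look: in about 1% of trials at true HR 0.80, 1-2% at 0.85 and 4-5% at 1.0.

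**The case against.** The best defence is that the rule does the job the design gives it. Section 11.1 treats a rise in 3-year DFS to 65-67% as meaningful. HR 0.72 is the 65% end of that range, and the rule stops only once it is excluded. The 62.7% implied by a lower limit of 0.78 falls short of it. A trial at the third-look boundary is also far from the observed hazard ratio of about 0.80-0.81 needed at the final analysis. In a one-sided superiority design, the conclusion could be read as saying only that superiority was not shown. All of this supports the boundary, and that part stands. It does not support the sentence, which states a conclusion about extended dissection and is not limited to the effect tested.

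Three stronger readings might be inferred, and the documents do not support them.

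- **That the rule commonly stops a trial whose estimate favours extended dissection.** It can do so only at the third look, between about 0.98 and 1.00, and only if the 0.005 is one-sided. With the table's own 247 events the boundary is 0.999. At the first two looks the estimate must favour standard dissection.
- **That the plan dictates a published claim of no benefit.** The text speaks of evidence suggesting termination and a conclusion. Section 11.5 leaves termination and early reporting to the committee, and nothing bars reporting the hazard ratio with its interval.
- **That a smaller real benefit would be reported as none.** At a true hazard ratio of 0.85 the rule does not fire in about 86% of trials. The supported word is could.

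**Conclusion.** The point holds as a defect in the stated conclusion, of low to moderate weight. Crossing the futility boundary excludes a 28% reduction in the DFS hazard. It does not establish that extended dissection is no better than standard, because the 95% interval at the boundary still reaches down to about 0.78-0.83 (one-sided) or 0.80-0.87 (two-sided). If extended dissection truly raised 3-year DFS from 55% to about 60%, roughly one trial in seven (one-sided) or one in ten (two-sided) would stop under a rule whose attached conclusion is wrong.

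The figures assume exponential DFS, uniform accrual, no dropout and an unstratified test. The one-sided reading is the natural one for a directional rule, but it is an assumption. The core finding does not depend on it; only the possibility of stopping with an estimate just below 1 does. No fault is found in the boundary, the error rates or the committee's role.

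**What to change.** Keep the boundary. In Section 11.2, state whether the 0.005 futility test is one-sided or two-sided, and replace the attached conclusion with wording such as:

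> Crossing means that a 28% reduction in the DFS hazard (HR 0.72) has been excluded at the 0.005 level; the HR is reported with its confidence interval, and crossing does not by itself establish that extended dissection is no better than standard.

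This costs one reworded sentence and a stated sidedness. Boundary, power and sample size do not change if the sidedness stated is the one already intended. The downside is a less definite conclusion after a futility stop.
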